6.10.4.3. Infusion Site Reaction

The infusion site reactions will be searched by MedDRA PTs from all TEAEs. The number and percentage of patients experiencing at least one treatment-emergent infusion site reaction will be summarized and compared by treatment using Prescott's exact test.

For infusion site reactions identified by MedDRA PTs, the presence and severity of erythema, induration, pain, pruritus, and edema are collected on the eCRF and will be summarized for each treatment. There will be no statistical comparison between treatments.

6.10.4.4. Hepatobiliary Events

6.10.4.4.1. Treatment-Emergent Potential Hepatic Disorder

The percentages of patients with treatment-emergent drug-related hepatic disorder events will be summarized and compared by treatment using MedDRA PT nested within each SMQ, and ordered by decreasing frequency. The following SMQs based on MedDRA will be used to identify potential hepatic disorders:

- broad and narrow terms in the Liver related investigations, signs and symptoms SMQ (20000008)

- broad and narrow terms in the Cholestasis and jaundice of hepatic origin SMQ (20000009)
- broad and narrow terms in the Hepatitis non-infections SMQ (20000010)
- broad and narrow terms in the Hepatic failure, fibrosis and cirrhosis and other liver damage SMQ (20000013)
- narrow terms in the Liver-related coagulation and bleeding disturbances SMQ (20000015)

The percentage of patients with any 1 of the terms will be summarized, in addition to the percentages for each MedDRA PT. The percentages of patients with potentially drug-related hepatic disorders that lead to permanent study discontinuation will be summarized similarly.

6.10.4.5. Malignant Neoplasm Events

The Malignant tumors SMQ will be used to identify treatment-emergent malignant neoplasm event.

6.10.5. Clinical Laboratory Evaluation

The data from safety laboratory measures will be only collected at Visit 1 or Visit 4 for patient safety. Therefore, no by-treatment summary or statistical analysis will be provided.

6.10.6. Vital Signs and Other Physical Findings

Post-baseline measurements and change from baseline to post-baseline for vital signs (systolic blood pressure [SBP], diastolic blood pressure [DBP], pulse rate) and physical characteristics (weight, BMI) at the scheduled visits will be summarized by week (relative to the start of each randomized treatment period) for patients who have both baseline and at least 1 post-baseline result.

The measurements during the treatment period (0 to 4 weeks during each randomized treatment period) will be analyzed by MMRM model with treatment, baseline value of the response variable, sequence, period, week (defined from the start of each randomized treatment period), and week by treatment interaction as fixed factors and patient as the random factor.

Change from the minimum value during the baseline period to the minimum value during the 2 randomized treatment periods for vital signs and physical characteristics will be summarized by treatment for patients who have both baseline and at least 1 post-baseline result. Baseline will be the minimum of nonmissing observations in the baseline period. The minimum value in the treatment period will be analyzed. Similarly, change from the maximum value during the baseline period to the maximum value during each of the 2 randomized treatment periods (Period I and Period II) for vital signs and physical characteristics will be summarized by treatment for patients who have both baseline and at least 1 post-baseline result. Baseline will be the maximum of nonmissing observations in the baseline period. The maximum value in the treatment period will be analyzed. Planned and unplanned measurements will be included in the analysis.

The percentages of patients with treatment-emergent high or low vital signs and weight at any time after randomization during each of the 2 randomized treatment periods (Period I and Period II) will be summarized and compared between treatments using Prescott's exact test for patients who have both baseline and at least 1 postbaseline measurement. A treatment-emergent high result is defined as a change from a value less than or equal to the high limit at all baseline visits to a value greater than the high limit at any time that meets the specified change criteria during the 2 randomized treatment periods. A treatment-emergent low result is defined as a change from a value greater than or equal to the low limit at all baseline visits to a value less than the low limit at any time that meets the specified change criteria during the 2 randomized treatment periods. [Table ITSM.6.5](#) will be used to define the low and high limits and change thresholds.

Table ITSM.6.5. Categorical Criteria for Abnormal Treatment-Emergent Blood Pressure and Pulse Measurement, and Categorical Criteria for Weight Changes for Adults

Parameter	Low	High
Systolic BP (mm Hg) (Supine or sitting – forearm at heart level)	≤ 90 and decrease from baseline ≥ 20	≥ 140 and increase from baseline ≥ 20
Diastolic BP (mm Hg) (Supine or sitting – forearm at heart level)	≤ 50 and decrease from baseline ≥ 10	≥ 90 and increase from baseline ≥ 10
Pulse (bpm) (Supine or sitting)	< 50 and decrease from baseline ≥ 15	> 100 and increase from baseline ≥ 15
Weight (kg) (Consistent clothing and timing in relationship to meals and voiding)	(Loss) decrease $\geq 7\%$	(Gain) increase $\geq 7\%$

Abbreviations: BP = blood pressure.

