Week of Treatment	-3	-2	-1	0	*	2	4	*	6	8	10	
Visit Window (±days)	0	3	3	3	3	3	3	3	3	3	7	
Study Logistics												
Informed consent signed	X											
Eligibility Criteria Reviewed	X	X										
Randomization				X								
IWRS	X	X	X	X	X	X	X	X	X	X	X	X
Crossover							X					
Clinical Assessments												
Patient demographics	X											
Medical history and preexisting conditions	X											
Physical examination/height	X											
ECG (12-lead) ^b	X											
Body weight	X	X		X			X			X	X	X
Vital signs: blood pressure/pulse rate ^c	X	X		X			X			X	X	X
Concomitant medication	X	X	X	X	X	X	X	X	X	X	X	X
Adverse events		X	X	X	X	X	X	X	X	X	X	X
Patient Education and Management												
Set standardized high/low glucose alerts		X		X			X					
At screening, record pump bolus delivery speed (Standard [1.5 U/min] or Quick [15 U/min]). At other office visits, confirm and record pump bolus delivery speed unchanged from screening.	X	X		X			X			X		
At screening, record infusion set cannula length (6mm or 9mm). If changed during study, record infusion set cannula length (6mm or 9mm) and reason for change.	X	X		X			X			X		
Reset pump ISF, CR, and AIT to randomization settings							X					
Change infusion set and reservoir at investigative site ^d		X		X			X			X ^e		X ^e

	Screening	Lead-In		Study Period I				Study Period II			Safety Follow-up	Early Termination
Visit	1	2	3a	4	5a	6a	7	8a	9a	10	801	ET
Week of Treatment	-3	-2	-1	0	*	2	4	*	6	8	10	
Visit Window (±days)	0	3	3	3	3	3	3	3	3	3	7	
Review/Answer questions on Medtronic 670G System, Diabetes management education, carbohydrate counting, collecting 4-point SMBG profiles, and review hypoglycemia and hyperglycemia management guidelines ^{f,g}		X										
Review total daily insulin dose ^h	X											
Review pump, CGM, and SMBG data for use in clinical decision making		X	X	X	X	X	X	X	X	X		X
Review/discuss hypoglycemia data			X	X	X	X	X	X	X	X	X	X
Remind patient to upload pump data to CareLink weekly		X	X	X	X	X	X	X	X	X		
Ancillary Supplies/Diaries/IP												
Dispense infusion sets, reservoirs, BG test strips, and ancillary supplies		X		X			X			X	X	
Dispense Study Diary		X		X			X			X		
Collect Study Diary and review with patient				X			X			X	X	X
Start open-label Humalog at office visit		X										
Start non-study rapid-acting analog insulin at office visit										X		
Dispense IP				X			X					
Collect used and unused study drug and supplies from patient				X			X			X		X
Transfer Diary Data to eCRF												

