Pump factors - CR, ISF, and AIT ^b	All patients in the Randomized Population with a baseline and at least one post-baseline observation	Last value of Visits 2-4 prior to or on the date of the first dose of IP	Last observation 1 day prior to Visit 7 and last observation 1 day prior to Visit 10 prior to last dose in IP of each randomized treatment period (Period I and Period II) excluding data (if any) that are collected while patients temporarily are off pump or off IP

Baseline and Post-Baseline Definitions and Patient Population by Study Period and Type of Analysis

Study Period/Analysis	Patient Population	Baseline Observations	Post-Baseline Observations
4-Week of Each Randomized Treatment Period Regardless of IP use (from randomization to Week 4 of each randomized treatment period regardless of IP use)			
TEAEs	Randomized Population	Prior to first dose of randomized IP (or Visit 4 if the dose date is missing)	Each 4-week randomized treatment period regardless of IP use
Weight and vital signs	All patients in the Randomized Population with a baseline and a post-baseline observation	Last of Visits 2-4	Visits 7 and 10 regardless of IP use
Week 2-4 of Each Randomized Treatment Period while on IP			
CGM outcome variables	All patients in the Randomized Population (with a baseline and a post-baseline observation for continuous variables, unless otherwise specified ^c)	From first to last dose of open-label Humalog, excluding data (if any) that are collected while patients temporarily are off pump or off open-label Humalog	From first to last dose of IP in each randomized treatment period (Period I and Period II), excluding data (if any) that are collected while patients temporarily are off pump or off IP
Week 2-4 of Each Randomized Treatment Period Regardless of IP			
Basal, bolus, and total insulin doses, bolus/total insulin dose ratios ^d	All patients in the Randomized Population with a baseline and a post-baseline observation	Last of Visits 2-4	Visits 7 and 10 regardless of IP use
Basal, bolus, and total insulin doses, bolus/total insulin dose ratios by infusion set wear day, by meal, and by infusion set wear day and meal ^e	All patients in the Randomized Population with a baseline and a post-baseline observation	Last of Visits 2-4	Last observed value before/at Visit 7 and before/at Visit 10 regardless of IP use

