observed from all associated LLTs mapping to the MedDRA PT during the corresponding randomized treatment period for the specified treatment. No statistical comparison between treatments will be conducted.

The number and percentage of patients who experienced a SAE including deaths and SAEs temporally associated or preceding deaths will be summarized by treatment using MedDRA PT (without regard to SOC). Events will be ordered by decreasing frequency within SOC. A listing of all SAEs (including data collected during the safety follow-up period) will also be provided.

The number and percentage of patients who discontinued from study in Period I and Period II due to an AE will be summarized by treatment using MedDRA PT (without regard to SOC). Events will be ordered by decreasing frequency. A listing of all AEs as reason for study discontinuation will also be provided.

For events that are gender-specific (as defined by MedDRA), the denominator and computation of the percentage will include only patients from the given gender.

Table ITSM.6.3 summarizes the planned analyses and the requirement of analysis data for different analysis periods.

Table ITSM.6.3. Adverse Event Analysis Periods

Analysis Period	Analysis Population	Analysis	IP USE	Treatment
Lead-in Period	Enrolled Population	AE overview; TEAE by PT; SAE, discontinuation due to AE	N/A	Open-label Humalog
Treatment Period (0-8 Weeks)	Randomized Population	AE overview; TEAE by PT nested within SOC and by PT; TEAEs by maximum severity; SAE; discontinuation due to AE; other notable AEs	All data regardless of IP use	LY900014, Humalog
Safety Follow-up Period	All patients in the Randomized Population who enter follow-up period	TEAE by PT	All data	Overall ^a

Abbreviations: AE = adverse event; IP = investigational product; N/A = not applicable/available; PT = preferred term; SAE = serious adverse event; SOC = system organ class; TEAE = treatment-emergent adverse event.

^a overall means that data will be summarized in total and no by-treatment summary or statistical analysis will be included.

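### Treatment-emergent vital-sign percentages in SAP 6.10.6 include patients who cannot have the event; an at-risk denominator would be a small descriptive improvement

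*SAP*

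**What the plan says.** SAP 6.10.6 states that the percentages of patients with treatment-emergent high or low vital signs and weight "will be summarized and compared between treatments using Prescott's exact test", and it takes them "for patients who have both baseline and at least 1 postbaseline measurement". No other condition is placed on the analysis set. Table ITSM.6.2 gives the same population for weight and vital signs.

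The event definition is narrower. On the high side: "A treatment-emergent high result is defined as a change from a value less than or equal to the high limit at all baseline visits". The low side mirrors it, requiring "a change from a value greater than or equal to the low limit at all baseline visits". Table ITSM.6.5 adds a minimum change. For systolic pressure the high criterion is 140 mm Hg with a rise of at least 20. Weight has only a 7% change criterion and no absolute limit.

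The Schedule of Activities (Protocol Section 2, row "Vital signs: blood pressure/pulse rate") places measurements at Visits 1, 2 and 4 before randomized treatment. It then gives one scheduled measurement per treatment period, at Visit 7 and Visit 10, apart from early termination. Table ITSM.6.2 sets the vital-sign baseline as "Last of Visits 2-4".

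**The concern.** The numerator and the denominator describe different groups. A patient with one baseline systolic reading above 140 mm Hg can never be a treatment-emergent high, whatever happens on treatment, yet is counted among those without the event. The same holds for each blood pressure and pulse limit in each direction. The listed eligibility criteria set no blood pressure or pulse limit, so such patients can be enrolled.

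The reported percentage is therefore diluted as a measure of risk among patients who could have the event, and the dilution runs in the reassuring direction. It differs from row to row, because the share beyond a limit at baseline differs by parameter and direction. No at-risk count is planned, so a reader of the table cannot see how large it is. The SAP does apply the at-risk idea elsewhere: for gender-specific adverse events, "the denominator and computation of the percentage will include only patients from the given gender".

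**Working it through.** **Stated figures.** The documents give no figure for treatment-emergent vital signs or for the number beyond a limit at baseline. The only number used from them is the planned size, about 42 randomized (SAP 5.2), as the denominator N.

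**Step 1: the identity.** Let x be patients with an event, N the SAP denominator, k the patients beyond the limit at any baseline visit, and q = k/N.

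- SAP percentage = x/N
- At-risk percentage = x/(N − k)
- Ratio of the two = 1 − k/N = 1 − q

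This is exact and needs no model. For N = 42 and an assumed x = 4:

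| k (assumed) | SAP % | At-risk % | Ratio |
|---|---|---|---|
| 0 | 9.5 | 9.5 | 1.00 |
| 4 | 9.5 | 10.5 | 0.90 |
| 8 | 9.5 | 11.8 | 0.81 |
| 12 | 9.5 | 13.3 | 0.71 |

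**Step 2: a plausible q for high systolic.** Assumptions, none from the documents: each reading is a patient mean plus visit noise, both normal, with between-patient SD 12 and visit-to-visit SD 8. Then q is the probability that at least one baseline reading exceeds 140.

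For one reading the total SD is √(144 + 64) = 14.4, so a mean of 120 gives P(Z > 20/14.4) ≈ 8%. For two readings (Visits 2 and 4, the measurements within the Table ITSM.6.2 window) q was simulated.

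| Mean (mm Hg) | q, one reading | q, two readings |
|---|---|---|
| 120 | 8% | 13% |
| 125 | 15% | 22% |
| 130 | 24% | 34% |

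For low systolic, the same assumptions put only about 0.5% to 3% of patients below 90 at either reading, so that row would hardly change.

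**Step 3: the size in percentage points.** The absolute gap is the at-risk percentage times q, so it depends on how common events are. An event needs both baseline readings at or below 140, and an on-treatment reading above 140 that is at least 20 above the last baseline value. With one scheduled reading per period and no treatment effect, simulation under the same assumptions gives:

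| Mean (mm Hg) | SAP % | At-risk % = SAP %/(1 − q) | Gap (points) | Expected events in 42 |
|---|---|---|---|---|
| 120 | 0.80 | 0.92 | 0.12 | 0.34 |
| 125 | 1.09 | 1.40 | 0.31 | 0.46 |
| 130 | 1.28 | 1.95 | 0.67 | 0.54 |

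The expected gap is below 1 percentage point throughout.

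**Step 4: the treatment comparison.** Patients beyond the limit at baseline have no event in either period, so they score 0 in Prescott's test. The exact test was computed with all 42 patients and with 30 at risk (k = 12), splitting events as evenly as possible between sequences:

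| Events on LY900014 only / Humalog only | p, all 42 | p, 30 at risk |
|---|---|---|
| 6 / 0 | 0.0337 | 0.0349 |
| 4 / 0 | 0.1313 | 0.1341 |
| 5 / 1 | 0.2211 | 0.2222 |

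**Step 5: who is at risk is itself unsettled.** Table ITSM.6.2 points to one last value, while the event definition uses all baseline visits. If only one reading counted, q would fall to the first column of Step 2. The text also requires a value strictly beyond the limit, whereas Table ITSM.6.5 includes the limit itself for systolic and diastolic pressure. A baseline systolic of exactly 140 is within the limit by the text and meets the high threshold by the table. For pulse the two agree.

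**The case against.** The strongest reply is that this is a choice of denominator and not a mistake. The share of all evaluable treated patients with a new abnormality is a valid crude incidence. It is too low only for a reader who wants the risk among patients within the limit at baseline. That stands, and it is why the point is a matter of presentation. The SAP's adverse-event percentages likewise keep patients who had the condition at baseline. The parallel is partial, though: under SAP 6.10.2 such a patient can still count by worsening, whereas the vital-sign definition closes that route.

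The second reply is that these patients are not lost to the safety review. SAP 6.10.6 also plans change from baseline by week, a repeated-measures model, and change from the baseline maximum (and minimum) to the maximum (and minimum) on treatment, including unplanned measurements. None of these excludes patients already beyond a limit, so a further rise appears there. This also stands.

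Third, the safety objective is comparative and exploratory, and in a crossover the same patients contribute to both treatments. Both percentages shrink by nearly the same factor, and Step 4 shows the test is essentially unchanged. A reader might infer that the dilution biases the comparison of LY900014 with Humalog; the design and the definitions do not support that.

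**Conclusion.** The mismatch is real on the text, and nothing else in the SAP or protocol repairs it. Its consequence is small. Each blood pressure and pulse percentage is (1 − q) times the at-risk percentage, with q unknown and different for each row, and zero where nobody is beyond the limit at baseline. Under the stated assumptions q for high systolic is about 13% to 34% with two baseline readings, with an expected difference under 1 percentage point absent a treatment effect. If more events occurred, the gap would grow in proportion, as Step 1 shows. Diastolic pressure and pulse were not modelled. Weight is not affected.

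A reader might infer a much larger distortion, for example three events shown as 3/42 = 7.1% when the at-risk figure is 3/(42 × 0.596) = 12.0%. That needs a mean of 130 mm Hg, a q of about 40% that arises only if Visit 1 counts as a third baseline reading, and three events where the same model expects about half of one. Table ITSM.6.2 confines the baseline to Visits 2 to 4; with two readings the figure would be 3/(42 × 0.656) = 10.9%, still resting on three events. The documents do not support presenting such a contrast as the likely effect.

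**What to change.** In SAP 6.10.6, for each blood pressure and pulse parameter and each direction, define the denominator as patients within that limit at all baseline visits who have at least one post-baseline value in the period concerned. Show it in the table as N at risk. Keep all patients with baseline and post-baseline data for weight.

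In the same edit, state which visits count as baseline for this definition, so that it agrees with Table ITSM.6.2. Also make the text and Table ITSM.6.5 agree on whether a blood pressure exactly on the limit counts as beyond it.

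The cost is a few lines of SAP wording and one filter in the program, with no new data. The downside is that denominators will differ between rows and the percentages will be slightly less favourable. Where nobody is beyond a limit at baseline, the percentage does not change.

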6.10.7. Pump-related Safety Analyses

The protocol requires that patients change infusion set every 3 days, unless a change is required for failure of the infusion set in which case an unplanned infusion set change with noted reason needs to be reported in the patient's study diary and transferred to the eCRF. Accordingly, all infusion set changes captured in the CareLink raw data will be classified into 2 categories: planned and unplanned. An infusion set change will be classified as "unplanned" if there is an unplanned infusion set change reported in eCRF linked by time (within a 12-hour window, considering the fact that the patient-reported infusion set change time for eCRF could be slightly off the precise change time stored in the CareLink raw data). Other infusion set changes will be classified as "planned".

If there are unplanned infusion set changes reported in the eCRF that do not have linked records in the Carelink raw data (potentially due to misreporting), these records will be excluded from the calculation of time until infusion set changes and will be reported in the Electronic Trial

Master File (eTMF) as permanent data issues. To be conservative, these infusion set changes will be still included in the analysis of rate and incidence of unplanned infusion set changes.

The incidence (percent of patients with at least 1 event) and rate will be analyzed using Prescott's exact test and Wilcoxon signed-rank test, respectively for planned, unplanned infusion set changes for any reason and for each individual reason (pump occlusion alarm, unexplained high BG, infusion site reaction [pain, redness or swelling at infusion site], infusion set problem [infusion set kinked, pulled out, leaking, reservoir empty, etc.]), by overall (across all infusion set wear days) and by infusion set wear day (Day 1, Day 2, and Day 3).

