7.2. Method of Treatment Assignment

Patients who meet all criteria for enrollment and complete the lead-in period will be randomized to double-blind treatment at Visit 4. Assignment to treatment sequences will be determined by a computer-generated random sequence using an interactive web-response system (IWRS).

Patients will be randomized to 1 of the 2 treatment sequences in a 1:1 ratio:

Sequence A: LY900014 → Humalog

Sequence B: Humalog → LY900014

Stratification will be by HbA1c stratum ($\leq 7.0\%$, $> 7.0\%$ at Visit 1) and percentage of time with SG values from 70 to 180 mg/dL over the 2 weeks prior to randomization ($\leq 75\%$, $> 75\%$).

Patients will begin using a new reservoir and infusion set prior to leaving the investigative site at Visits 2, 4, 7 and 10. Patients will change the pump reservoir and infusion set every 3 days unless a change is required due to a failure of the infusion set.

The IWRS will be used to assign all study treatment during the study, including Humalog during the lead-in period. The IWRS will be used to assign vials containing double-blind IP to each patient randomized to the treatment sequences. Site personnel will confirm that they have located the correct vials by entering a confirmation number found on the vials into the IWRS.

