9.1.4.3. Infusion Set Changes

Patients should change their infusion set and reservoir every 3 days.

The patient's study diary will be used to collect unplanned infusion set changes, including date and time of change and the primary reason for unplanned change.

- Pump occlusion alarm,
- Unexplained high BG,
- Infusion site reaction (pain, redness or swelling at infusion site), or
- Infusion set problem (infusion set kinked, pulled out, leaking, reservoir empty, etc.).

Unexplained hyperglycemia is defined as high BG >300 mg/dL that cannot be explained by a missed prior bolus, dietary indiscretion, rebound or treatment of hypoglycemia, a pump failure, an empty pump reservoir, an infusion set complication (for example, kinked, came out, leaking), or an infusion site complication (for example, pain, redness).

Investigators will review pump occlusion alarms, unexplained hyperglycemia, and unplanned infusion set changes with patients at each visit.

Any interruption of CSII will need to be documented in the eCRF. When patients resume use of pump following the interruption, the infusion set change should not be entered as an unplanned infusion set change in the study diary.

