9. To compare LY900014 and Humalog with respect to the percentage of time with sensor glucose values within range (70 and 140 mg/dL)	9. percentage of time with sensor glucose values between 70 and 140 mg/dL (inclusive), during the last 2 weeks of each 4-week treatment period
10. To compare LY900014 and Humalog with respect to the rate and incidence of unplanned infusion set changes	10. Rate (events/patient/30 days) and incidence of unplanned infusion set changes by reason (Pump occlusion alarm, Suspected infusion set occlusion (unexplained high BG), Infusion site reaction (pain, redness or swelling at infusion site), Infusion set problem (infusion set kinked, pulled out, leaking, reservoir empty, etc.), during the 4-week treatment period
11. To compare LY900014 and Humalog with respect to the percentage of time with sensor glucose values in hyperglycemic glucose ranges	11. Percentage of time with sensor glucose values >180 mg/dL and >250 mg/dL, during the last 2 weeks of each 4-week treatment period

Objectives and Endpoints

Objectives	Endpoints
12. To compare LY900014 and Humalog with respect to the 1-hour postprandial sensor glucose excursions	12. Mean 1-hour postprandial sensor glucose excursions (mean sensor glucose measured 1 hour after the start of the meal minus mean sensor glucose at the start of meal) after breakfast, during the last 2 weeks of each 4-week treatment period
13. To compare LY900014 and Humalog with respect to the within-patient sensor glucose variability	13. Coefficient of variation (CV) (standard deviation/mean) of sensor glucose values, during the last 2 weeks of each 4-week treatment period
14. To evaluate HbA1c of LY900014 and Humalog	14. Summary statistics of actual and change of HbA1c during each 4 week treatment period
15. To evaluate 1,5-AG of LY900014 and Humalog	15. Summary statistics of actual and change of 1,5-AG during each 4-week treatment period
16. To compare LY900014 and Humalog with respect to the factors affecting dosing in pumps	16. Actual and change from baseline in factors affecting dosing in pump (breakfast CR, AIT, breakfast ISF), during the 4-week treatment period

Abbreviations: 1,5-AG = 1,5 Anhydroglucitol; AIT = active insulin time; BG = blood glucose; CR = carb ratio; HbA1c = hemoglobin A1c; ISF = insulin sensitivity factor.

5. Study Design

[figure not shown]

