6.10.7.1. Time until Infusion Set Changes

Date and time of all infusion set changes will be captured in the CareLink raw data. Time interval until infusion set change for each infusion set can be derived based upon the CareLink raw data by calculating the time difference (hours) between the infusion set change and its previous infusion set change.

For each treatment period (lead-in, Period I and Period II), time interval until infusion set change (overall, planned, unplanned, or unplanned due to unexplained high BG) will be derived by averaging across the corresponding infusion set changes that occur within the period. The analyses for time interval (overall and planned) will be then conducted by an MMRM model similar to that for the primary endpoint. Time interval until unplanned infusion set change due to unexplained high BG will be summarized by treatment. No treatment comparison will be conducted due to the low occurrence.

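### Pump-recorded set changes with no linked diary report count as planned whatever their wear, so missed diary entries lower the exploratory any-reason unplanned count and enter the tested planned wear time

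*SAP*

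**What the plan says.** SAP 6.10.7 sorts all set changes in the CareLink raw data into two classes. A change is unplanned "if there is an unplanned infusion set change reported in eCRF linked by time (within a 12-hour window", the window allowing for inexact patient-reported times. Everything else follows a default: "Other infusion set changes will be classified as" planned. No minimum wear, occlusion-alarm check or glucose check limits that default.

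The eCRF report comes from the patient's diary, which under Protocol 9.1.4.3 "will be used to collect unplanned infusion set changes, including date and time of change", together with the main reason. Protocol Appendix 3.2.1 describes diary data as a paper source transcribed by the site. The schedule against which a change is early is in Protocol 7.2: "Patients will change the pump reservoir and infusion set every 3 days unless a change is required due to a failure of the infusion set".

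SAP 6.10.7 does foresee disagreement between diary and pump, in one direction. Reports with no CareLink record are left out of the wear-time calculation, but: "To be conservative, these infusion set changes will be still included in the analysis of rate and incidence of unplanned infusion set changes".

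The classification feeds these analyses:
- Endpoint 10, listed as tertiary/exploratory in SAP Table ITSM.4.1: "Rate (events/patient/30 days) and incidence of unplanned infusion set changes by reason". SAP 6.10.7 adds an any-reason comparison.
- Rate and incidence of planned and unplanned changes, overall and by wear day (SAP 6.10.7).
- Wear time (SAP 6.10.7.1): "The analyses for time interval (overall and planned) will be then conducted by an MMRM model similar to that for the primary endpoint".

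SAP 6.1 removes data from temporary spells off pump or off study insulin from these analyses.

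**The concern.** CareLink time-stamps every set change, but only the diary can make one unplanned. Suppose a patient changes a set at home after 30 hours and does not write it down. The pump record shows a change well before 72 hours, and the SAP counts it as planned. A diary report without a pump record has an explicit cautious rule. A short-wear pump record without a diary report has none.

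Two results are exposed. The any-reason unplanned rate and incidence fall, and the absolute difference between treatments shrinks with them. Planned wear time takes in failed sets, so a true difference in set failure could appear as a difference in planned wear. Protocol 3.3 lists occlusion alarms, and unexplained hyperglycemia that leads to unplanned set changes, among the safety evaluations, so the comparison has a purpose even though it is exploratory.

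**Working it through.** The plan states no figure on this point, so there is none to reproduce. The check has two parts: what happens to each type of record, and how large the effect could be.

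**1. Where each record goes (SAP 6.10.7 and 6.10.7.1)**

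| Record | Unplanned rate and incidence | Planned wear time |
|---|---|---|
| Pump change with linked report | counted | not included |
| Report with no pump record at all | counted | not included |
| Report whose pump record lies outside the 12-hour window | counted | pump record included |
| Early pump change, no report | not counted | included |

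The last row is the gap. The third row affects planned wear only.

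**2. Size, by illustration**

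From the documents: a 28-day period (672 h) and scheduled wear of 72 h. Assumed, because the documents give no values: true failures per period k = 0.5 to 2; wear of a failed set w = 24 to 48 h; share unreported u = 10% to 50%; all other sets worn exactly 72 h; Poisson counts for incidence.

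- Observed rate per 30 days = k(1−u) × 30/28
- Observed incidence = 1 − exp(−k(1−u))
- Genuinely planned sets P = (672 − kw)/72
- Observed planned wear = (72P + wku)/(P + ku)

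For k = 1 and w = 36 h, P = 636/72 = 8.83. At u = 25% the rate is 0.75 × 30/28 = 0.80, and planned wear is (636 + 9)/(8.83 + 0.25) = 71.0 h.

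| u | Rate per 30 days | Incidence | Planned wear (h) |
|---|---|---|---|
| 0 | 1.07 | 63% | 72.0 |
| 10% | 0.96 | 59% | 71.6 |
| 25% | 0.80 | 53% | 71.0 |
| 50% | 0.54 | 39% | 70.1 |

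Over the whole assumed range, observed planned wear lies between 71.9 h (k = 0.5, w = 48, u = 10%) and 67.0 h (k = 2, w = 24, u = 50%).

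**3. Between treatments**

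Take k = 2 on one treatment and 1 on the other, w = 36 h, and the same u on both. True planned wear is 72 h on each.

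| u | Rate difference per 30 days | Rate ratio | Spurious planned-wear difference (h) |
|---|---|---|---|
| 0 | 1.07 | 2 | 0 |
| 10% | 0.96 | 2 | 0.44 |
| 25% | 0.80 | 2 | 1.05 |
| 50% | 0.54 | 2 | 1.93 |

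Overall wear is 672/(P + k): 65.0 h for k = 2 and 68.3 h for k = 1, whatever u is.

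**4. Short wear that is not a failure**

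Nine 72-hour sets use 648 h of a 672-hour period, so a patient exactly on schedule reaches Visit 7 with a set worn 24 h, and it is changed at the site. Changes on resuming the pump after a CSII interruption are also properly kept out of the diary (Protocol 9.1.4.3). A bare wear cut-off would count both as missed failures.

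**The case against.** Much can be said for the plan as written.

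- **Early planned changes are not hidden.** SAP 6.10.7 already tests rate and incidence of planned changes by wear day, and a 30-hour change would appear as planned on Day 2. This stands, with limits. Days 1 and 2 also hold site-visit and convenience changes, and a change between 48 and 60 hours falls in Day 3 with the scheduled ones. The detailed listing in SAP 6.10.7.2 covers unplanned changes only.
- **Overall wear time is tested too** and does not depend on the diary. This stands fully.
- **Counting from the diary has a logic.** Endpoint 10 is defined by reason, and only the diary gives a reason. No reanalysis can recover by-reason rates for unreported changes. This stands; the any-reason count is what can be examined.
- **Other checks exist.** Sites review unplanned changes with patients at visits (Protocol 9.1.4.3), review CareLink uploads weekly (SAP 5.1), and look at both diary and CareLink for compliance (Protocol 7.6). These may reduce under-reporting, but none requires short-wear pump records to be reconciled with the diary.

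A reader might infer that the default favours LY900014. The documents do not support this: the same rule applies to both treatments in a double-blind crossover, and equal under-reporting pulls the absolute difference towards zero without altering the ratio. Nor do they support treating every short unlinked change as a missed failure, as step 4 of the working shows.

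**Conclusion.** The gap is real and modest. An on-pump, on-study-insulin CareLink change without a linked report is planned whatever its wear, and no written step catches an early home change that the diary missed. Such changes lower the any-reason unplanned rate and incidence and mix into the tested planned wear time.

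The size is unknown. At one failure per 28 days, 36 hours of wear and 25% unreported, the rate loses 0.27 per 30 days (1.07 to 0.80) and planned wear about 1 hour. All three inputs are assumptions, so the figures show direction and scale only. If the unreported share is equal on both treatments, which blinding makes plausible, the rate ratio is unaffected. The absolute rate difference still shrinks and a spurious planned-wear difference can still arise. Overall wear time does not change.

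A reader might go further and take this as a threat to the trial's main conclusion. It is not: endpoint 10 is exploratory, and the primary analysis of time in range does not use this classification.

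**What to change.** Keep the main analyses in SAP 6.10.7 and 6.10.7.1 as written and add:

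1. A flag, early with reason not recorded, for CareLink changes after less than 60 hours of wear that have no linked eCRF report. Exempt changes made at the site (Visits 2, 4, 7, 10 and early termination) and changes on resuming the pump after a CSII interruption.
2. A table of flagged changes by treatment.
3. A sensitivity analysis of any-reason unplanned rate and incidence that counts them.
4. A sensitivity analysis of planned wear time that leaves them out.

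In the illustration (k = 1, w = 36 h, u = 25%), item 3 returns the rate from 0.80 to 1.07 per 30 days and item 4 returns planned wear from 71.0 to 72 h.

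The cost is a few lines of SAP text and some programming, with no new data collection. There are three drawbacks. Some convenience changes will enter the sensitivity count. The 60-hour limit is borrowed from the by-wear-day analyses in SAP 6.1, where it secures enough data per day; it is not a failure criterion. And item 4 selects on the variable being analysed, so its mean is biased upward. It should be read as a bound and should not replace the main planned-wear analysis.
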